2.3 Data management

Most data is collected and managed using REDCap, an electronic data capture system. The REDCap system includes validation rules for data entry to help ensure data accuracy, and has a full audit trail of data entry and changes. Data will be transcribed into REDCap from the original source (e.g. Cerner electronic medical records) and queries will be raised for inconsistent, impossible or missing data.

2.4 Missing data

For the primary analysis, there will be no data imputation for missing data in the primary endpoint.

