The coagulopathy is particularly noteworthy given an early increase in D-dimer has very high positive predictor value for death in COVID-19, and D-dimer concentrations are unusually high in COVID-19, over and above what would be expected for an acute phase response in an unwell patient (Tang (a), Tang (b)). Given the pleiotropic effects of AngII and Ang(1-7) on the components of the coagulation system, overactivation of the renin-angiotensin system may partly drive dysregulation of coagulation. We therefore hypothesise that the coagulopathy associated with COVID-19 is partly explained by both AngII accumulation and Ang(1-7) deficiency. Importantly, whilst ACEI and ARB treatment will antagonise AngII accumulation, they not only fail to address Ang(1-7) deficiency, but would in fact worsen it. This is because ACEI will further deplete Ang(1-7) production, over and above that caused by ACE2 internalization (Luque), and whilst an ARB will not further deplete Ang(1-7), it will prevent it from binding AT1R and hence block its beneficial actions via this receptor. Hence neither ACEi nor ARBs are appropriate tools to address this hypothesis in the context of COVID-19 infection

TRV027 is a similar peptide to Ang(1-7) but is a much more potent biased agonist at AT1R than Ang(1-7), potently and selectively recruiting β -arrestin to the AT1R while antagonizing Ang II-stimulated Gq activation (Violin). This β -arrestin bias of the ligand translates into unique downstream signaling, including extracellular signal-regulated kinases 1 and 2 (ERK1/2) phosphorylation and AT1R internalization. Recruitment of β -arrestin by TRV027 stimulates the activation of endothelial cell nitric oxide synthase (eNOS) and prostacyclin production (Violin). The combination of inhibition of Ang-II-mediated G-protein activation and activation of eNOS and prostacyclin production may contribute to the in vivo vasodilatory properties of TRV027 (Violin). ***In summary, TRV027, a biased agonist at AT1R, would be expected to oppose the effects of AngII accumulation, and functionally correct the Ang(1-7) deficiency.*** Hence it is an appropriate tool to examine the link between RAS activation and coagulopathy in the context of COVID-19 infection.

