4.4 WITHDRAWAL CRITERIA

Based on current outcome statistics, many subjects are likely to progress to end organ failure resulting in Intensive Therapy Unit (ITU) admission or death. Admission to ITU is therefore expected and will not result in withdrawal of the subject. Provision for informed consent of participants lacking capacity are specified in **sections 4.3 and 8.2**.

Subjects may withdraw from the study at any point, without giving a reason. If the subject loses capacity, the clinician in charge of their care can elect to withdraw the subject if they deem it clinically appropriate to do so.

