8.2 CONSENT

Consent to enter the study must be sought from each participant only after a full explanation has been given, an approved participant information sheet provided and time allowed for consideration. Signed participant consent should be obtained before initiating any study procedures in patients that are capable of giving consent (refer to section 4.3 for further details). The right of the participant to refuse to participate without giving reasons must be respected. Participants that lack capacity may also be enrolled on the advice of a consultee (see section 4.3).

After the participant has entered the study the clinician remains free to give alternative treatment to that specified in the protocol at any stage if he/she feels it is in the participant's best interest, but the reasons for doing so should be recorded. In these cases the participants remain within the study for the purposes of follow-up and data analysis.

All participants are free to withdraw at any time from the protocol treatment without giving reasons and without prejudicing further treatment.

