2.2 Definition of population for analysis

The population for analysis will be the Full Analysis Set (FAS), which consists of all patients who received the full course of TRV027 or placebo. Patients who received at least 1 dose of TRV027 or placebo, but did not complete 3 days of infusion (Incomplete Analysis Set (IAS)) will be included in the baseline data set and summarised with descriptive statistics.

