2.5 Withdrawal from the study

Patients withdrawn from the study will still be included in the final analysis. Withdrawal can occur at any time according to the following reasons: Patient decision; toxicity, lost to follow-up; Death, or PI decision.

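### SAP 2.2, 2.4 and 2.5 together give patients who die or stop before the Day 3 sample no usable place in the primary comparison, and the resulting bias could run in either direction

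*SAP*

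**What the plan says.** Three sections of the SAP bear on a patient who does not reach Day 3 on treatment.

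- **SAP 2.2 (analysis population).** The analysis uses the Full Analysis Set, "which consists of all patients who received the full course of TRV027 or placebo". Patients who started but "did not complete 3 days of infusion (Incomplete Analysis Set (IAS)) will be included in the baseline data set and summarised with descriptive statistics".
- **SAP 2.4 (missing data).** The only rule is that "there will be no data imputation for missing data in the primary endpoint".
- **SAP 2.5 (withdrawal).** "Patients withdrawn from the study will still be included in the final analysis". Death is one of the listed reasons for withdrawal.

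Neither document gives a sensitivity analysis for the primary endpoint or a rule for death before the Day 3 sample.

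The protocol supplies the clinical premise. Section 1.1 says that "an early increase in D-dimer has very high positive predictor value for death in COVID-19", and section 4.4 says that "many subjects are likely to progress to end organ failure resulting in Intensive Therapy Unit (ITU) admission or death". It also says who stays in. On intensive care, section 4.4 states: "Admission to ITU is therefore expected and will not result in withdrawal of the subject". Where the clinician gives alternative treatment, section 8.2 states that "the participants remain within the study for the purposes of follow-up and data analysis".

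**The concern.** The primary endpoint is the change in D-dimer between Day 1 and Day 3. A patient who dies in that window has no change to analyse. A patient who stops the infusion early may still have a Day 3 value, because Protocol section 3 continues study assessments for 24 hours after an early stop, but SAP 2.2 sets that value aside. SAP 2.5 says such patients are included without saying how.

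On the documents' own premise, death is linked to a rising D-dimer, so the patients lost need not resemble those who remain. The comparison of those who remain is then not protected by randomisation. With 30 patients per arm, one to three such losses can move the estimate, and no planned analysis would show by how much.

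**Working it through.** **1. How the three sections act on each type of patient**

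| Patient | SAP 2.2 | SAP 2.4 | SAP 2.5 |
|---|---|---|---|
| Dies before the Day 3 sample | Descriptive only | No value, none imputed | Included, method not stated |
| Stops infusion early, Day 3 sample taken | Descriptive only, value unused | Not relevant | Included if withdrawn |
| Alive, no Day 3 sample | Depends on infusion received | No value, none imputed | Included if withdrawn |

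SAP 3.5 counts 72 hours of infusion as complete for the primary endpoint. Reading the full course in 2.2 as 72 hours rather than 7 days does not change the first two rows.

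**2. The plan's own figure**

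The plan states 30 per arm, 80% power, alpha 0.05 and a 30% reduction. It gives no SD and no sidedness, so 30 cannot be reproduced, only solved backwards. On the log scale (an assumption) the effect is −ln(0.70) = 0.357. For a two-sided test:

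SD = 0.357 / [(1.960 + 0.842) × √(2/30)] = 0.493

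Allowing for the rank test's efficiency of 0.955, SD = 0.493 × √0.955 = 0.482. I use 0.485, which lies between the two. It is an assumption, not a figure from the documents.

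**3. Strongest link: every rise above one cut-off is lost, same cut-off in both arms**

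Log change is taken as normal, with mean 0 on placebo and −0.357 on TRV027. If a share p of placebo is lost and z is the matching normal quantile, the observed means are:

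- placebo: −SD × φ(z)/(1 − p)
- TRV027: −0.357 − SD × φ(z′)/Φ(z′), with z′ = z + 0.357/0.485 = z + 0.735

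*p = 5% (1.5 placebo patients).* Placebo: −0.485 × 0.1031/0.95 = −0.053. TRV027: z′ = 2.380, 0.9% lost, mean −0.368. Difference −0.3155, so the estimated reduction is 1 − exp(−0.3155) = 27.1%.

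*p = 10% (3 placebo patients).* Placebo: −0.485 × 0.1755/0.90 = −0.095. TRV027: z′ = 2.017, 2.2% lost, mean −0.3825. Difference −0.288, so the estimated reduction is 25.0%.

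**4. Softer link, still common to both arms**

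The chance of loss is 1/(1 + exp[−(a + b·x/SD)]), where x is the log change, b is the log odds ratio per SD of rise, and a is set to give the stated placebo loss. The observed mean in each arm is the average of x weighted by the chance of being observed.

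| Odds ratio per SD | Estimate, 5% placebo loss | Estimate, 10% placebo loss |
|---|---|---|
| 2 | 29.6% | 29.2% |
| 3 | 29.1% | 28.4% |
| 5 | 28.6% | 27.5% |
| Cut-off (step 3) | 27.1% | 25.0% |

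**5. Other patterns of loss**

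- *Equal shares of the worst risers lost in each arm:* both means shift by the same amount, so the estimate stays at 30.0%. The same holds if loss depends on how the patient would have done without the drug.
- *Worst risers lost on TRV027 only:* at 5%, −0.357 − 0.053 = −0.409, an estimate of 33.6%. At 10%, −0.357 − 0.095 = −0.451, an estimate of 36.3%.
- *Softer link with extra loss on TRV027* (SD 0.493, slope 1 per SD, log-odds of loss one unit higher on TRV027, losses 10.5% and 13.1%): 30.7%.
- *Loss unrelated to outcome:* 30.0%. With SD 0.493, power falls from 80% to 78% at 5% loss and 76% at 10%.

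**The case against.** The case against making much of this is substantial.

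**Direction.** A reader might infer that the no-imputation rule shrinks a true effect. That needs more risers to be lost from placebo. The documents give no rate of missing Day 3 samples by arm, and step 5 shows zero or upward bias under other patterns. Loss on the drug arm is conceivable: Protocol 1.3 reports one earlier patient whose TRV027 infusion was stopped for hypotension. This objection stands.

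**Cause.** A reader might blame SAP 2.4 alone. SAP 2.2 already removes patients with under three days of infusion, so adding imputation would not bring them back. This stands. The converse also holds: widening 2.2 alone would still leave early deaths with no value under 2.4.

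**Illness.** A reader might infer that very ill patients miss the Day 3 sample. The documents do not say so; intensive care patients stay in the study. The outcome-related argument rests on death. The protocol expects many patients to reach intensive care or die, but gives neither a rate nor a timing, and the Day 1 to Day 3 window is only about two days.

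**Existing tables.** SAP Table 10 has the number of patients at Day 1 and Day 3 by arm, Table 2 counts patients with missed doses due to death or discharge, and Table 9 gives Day 30 survival. So the plan is not silent. But Table 10 covers only the Full Analysis Set, and none of these tables links a missing Day 3 value to its reason.

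**Power.** A reader might expect a worst-rank score to restore lost power. In simulation with the cut-off link, power is about 78% without loss, about 73% and 67% on observed data at 5% and 10% placebo loss, and about 78% with worst rank. That recovery is built in, because the values removed are exactly those then ranked worst. At an odds ratio of 3 per SD and 5% loss, observed-data and worst-rank power are 74.4% and 75.3%, with a standard error of about 0.7 points. The reason for worst rank is to give deaths a defined place, not to gain power.

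**Conclusion.** The gap is real. The three SAP sections do not agree on patients who die or stop before the Day 3 sample, and none provides a way to use them in the primary comparison. The documents' own link between D-dimer and death means the loss can be informative.

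The direction of bias is not established. It is toward no effect if a common rise-to-death mechanism acts and the drug works, nil with equal loss of the worst risers, and toward benefit if risers are lost more on TRV027. The size is unknown and probably small: under a common mechanism, about 0.4 to 3 percentage points off a true 30% reduction at 5% placebo loss, and about 0.8 to 5 points at 10%. These figures rest on an assumed SD, a log-normal model, assumed loss rates and an assumed link between rise and loss. SAP 3.2 does not say that D-dimer will be analysed on the log scale.

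The point merits a change to the SAP. It does not show that the primary result will be wrong.

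**What to change.** 1. Reconcile SAP 2.2 with 2.5. State which patients enter the primary comparison, and what inclusion means for a withdrawn patient with a Day 3 value, one without, and one who has died.
2. Add to SAP 2.4 a pre-specified sensitivity analysis of all dosed patients by randomised arm. Use every available Day 3 value whether or not the infusion was completed. In the rank comparison, give the worst rank to patients who die before the Day 3 sample.
3. Leave patients who are alive without a Day 3 value as missing in that analysis. Imputing those discharged before Day 3 from later samples is not workable, because Protocol section 3 schedules no later samples for them: its discharge provision covers Days 6 and 7 only, and Day 30 is a telephone call or record check.
4. Report this analysis beside the observed-data result, with a table of missing Day 3 values by arm and reason (death, discharge, withdrawal, other).

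The cost is some SAP wording, one extra analysis and one table, with no new data collection planned. The downside is that the worst-rank result describes a composite of D-dimer change and early death, so it should be labelled as such and not read as an effect on D-dimer alone.

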2.5 Withdrawal from the study

Patients withdrawn from the study will still be included in the final analysis. Withdrawal can occur at any time according to the following reasons: Patient decision; toxicity, lost to follow-up; Death, or PI decision.

2.6 Interim analysis

There is no plan to conduct any interim analysis.

2.7 Deviations from the SAP

Any deviation from the SAP, e.g. changes of handling and analysis methods of secondary variables following review of data during the study, will be reported in the final analysis report. If problems or fundamental issues become apparent in the on-going checking that forms part of the statistical analysis, the trial statistician will raise these with the appropriate individuals. Protocol deviations identified at any stage during the study will be documented and made available to the statistician and CI. Any such action and subsequent decisions will be documented in the final statistical analysis report.

3 Analysis Plan

3.1 Descriptive Analyses

The baseline characteristics of the patient cohort will be summarised according to section 2.1 (Table 1).

3.2 Efficacy data

DDimer levels will be measured at baseline and at 3 days. Differences in DDimer will be calculated for each patient, enabling an estimate of the mean difference and 95% confidence interval to be calculated for each treatment arm. The differences for the treatment groups will be compared using parametric or non-parametric tests as appropriate (Table 10). In addition, a 30% reduction in DDimer will be considered a response, and so the proportions responding (with 95% CI) will be calculated, and compared for the two groups (Table 11). The results of these two analyses will provide sufficient evidence to differentiate between statistical and clinical significance.

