3.1 STUDY OUTCOME MEASURES

Primary Endpoint

- Mean change from baseline D-dimer at day 1 to day 3 post randomisation

Exploratory Endpoints

- Assessed on days 1, 3, 5, and 8
 - Markers of dysregulation of coagulation system, e.g.
 - D-dimer, Coagulation profile
 - Markers of dysregulation of RAS, e.g.
 - Renin mass and activity (Day 1 only)
 - Markers of dysregulation of other systems, e.g.
 - SOFA score ((Pa/SaO₂)/FiO₂, GCS, Total bilirubin, platelets, creatinine, BP and inotrope requirement).

- Markers of dysregulation of the endocrine system
 - BNP, Troponin, Ferritin, LDH, Haptoglobin
 - Glucose
- Markers of Inflammation (i.e. Bacterial Sepsis)
 - Pro-calcitonin

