7. STATISTICS AND DATA ANALYSIS

This sample size (30 each group) provides 80% power (alpha 0.05) to detect a 30% change in D-dimer. Subjects will be block randomised based on age (<60, 60-69, >69 years) using a code generated by the trial statistician.

Mean change from baseline D-dimer at day 1-3 post randomisation (and exploratory variables) will be compared using paired or unpaired non-parametric methods as appropriate. The relationship between change from baseline and pre-treatment plasma renin will be investigated, on the basis that subjects with low renin (and hence greater RAS activation) would be predicted to have the greater response.

The aim of this study is to understand the relationship between the RAS, coagulopathy, and COVID-19. The results of this study have potential implications for studies which are currently being planned using RAS modulators (including TRV027) in COVID-19. Design decisions for these study need to be taken before this study will fully recruit. Hence, unblinded aggregate data, for those patients who have completed the dosing period, will be reviewed by the study team to help guide the design of these studies. Individual unblinded data will not be reviewed.

Data and all appropriate documentation will be stored for a minimum of 10 years after the completion of the study, including the follow-up period.

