2.1 Analysis Strategy

Histograms and boxplots will be used to check the distribution and possible outliers for continuous variables. Continuous variables will be summarised using medians and ranges. Categorical variables will be summarised using frequencies and percentages.

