3.7 Additional data

Vital signs and cardiovascular monitoring will be documented at days 1, 3 and 5. (Table 12).

Table 1. Baseline characteristics

	FAS		IAS	
	Control	TRV027	Control	TRV027
	Median (range) or N (%)			
Age (yr)				
Age group				
<60				
60-69				
>69				
Gender				
Male				
Female				
BMI (kg/m²)				
Ethnicity				
White				
Mixed				
Asian				
Black				
Other				
Disease severity?				
Ie FDA grade 1-5?				

Table 2 Drug Compliance

	Control N (%)	TRV027 N (%)
Total Missed doses		
Total % Compliance		
Median missed doses per patient (range)		
Patients with missed dose due to hospital discharge		
Patients with missed dose due to death		

Table 3 Safety data – Pooled Adverse events

	Control		TRV-027	
	No. of Events	No. of Subjects*	No. of Events	No. of Subjects*
Number of Adverse events				
Severity				
Grade 1				
Grade 2				
Grade 3				
Grade 4				
Grade 5				
Missing				
AE classification				
Not serious				
Serious				
AE expectedness				
Expected				
Unexpected				
Not Applicable				
Missing				
Relation to study				
Definitely				
Probably				
Possibly				
Unlikely				
Not related				
Not assessable				
Missing				

* A patient may have several AEs

Table 4 – TRV027 Safety data –Adverse events details by patient

Control				TRV-027			
Pt ID	AE category	AE name	Grade	Pt ID	AE category	AE name	Grade

Table 6 Safety data – Serious Adverse Events

	Control		TRV027	
	No. of Events	No. of Subjects	No. of Events	No. of Subjects
Number of Serious Adverse Events				
Reasons for SAE				
Resulted in death				
Life threatening				
Congenital anomaly/birth defect				
Persistent or significant				
Disability/incapacity				
Inpatient hospitalisation/prolongation of existing				
Other				
Severity				
Mild				
Moderate				
Severe				
Life threatening				
Death				
Causal relationship to study drug				
Definitely				
Probably				
Possibly				
Unlikely				
Not related				
Not assessable				

Table 7 Safety data – Serious Adverse events details (Controls)

SAE description	SAE Term	Outcome

Table 8 Safety data – Serious Adverse events details (TRV027)

SAE description	SAE Term	Outcome

Table 9 Day 30 Survival

	Control	TRV027
Alive		
Dead		
Lost to follow-up		

Table 10 FAS Efficacy and exploratory parameters

	Control			TRV027		
	Day 1 [N=] Median (range)	Day 3 [N=] Median (range)	Difference D3 – D1	Day 1 [N=] Median (range)	Day 3 [N=] Median (range)	Difference D3 – D1
D-dimer						
Platelets						
aPTT						
INR						
Fibrinogen						

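### The primary D-dimer test is described in two conflicting ways with no rule for choosing, ignores baseline and age stratum, and comes with no planned between-arm estimate

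*SAP*

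**What the plan says.** - **Endpoint.** Protocol 3.1 defines it as "Mean change from baseline D-dimer at day 1 to day 3 post randomisation". SAP 1.3 repeats this.
- **Test.** Protocol 7 and SAP 1.3 call for non-parametric methods, paired or unpaired. SAP 3.2 says: "The differences for the treatment groups will be compared using parametric or non-parametric tests as appropriate (Table 10").
- **Basis for choosing.** SAP 2.1 offers only this: "Histograms and boxplots will be used to check the distribution and possible outliers for continuous variables". Nothing links the plots to a test.
- **Estimate.** Per-patient differences are to be calculated, "enabling an estimate of the mean difference and 95% confidence interval to be calculated for each treatment arm". SAP 2.1 adds: "Continuous variables will be summarised using medians and ranges". Table 10 follows that for Days 1 and 3, then gives one column per arm headed "Difference D3 – D1". It has no between-arm column.
- **Target effect.** Protocol 7 states that 30 per group "provides 80% power (alpha 0.05) to detect a 30% change in D-dimer". SAP 1.5 words the same target as a reduction.
- **Relative scale.** SAP 3.2 adds a responder comparison in which "a 30% reduction in DDimer will be considered a response".
- **Randomisation.** Protocol 7 and SAP 1.5 block by age (<60, 60-69, >69 years). Age stratum appears in no planned comparison.

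**The concern.** Four gaps concern one analysis. The test is not fixed, so either of two tests would comply with the plan, and the deviation rule in SAP 2.7 would flag neither. The raw difference is an absolute quantity, while the effect the trial was sized for is proportional. Baseline D-dimer and age stratum are both available and neither is used. The plan also yields two within-arm intervals rather than an estimate of the treatment effect.

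The open choice matters more here than usual, because Protocol 7 lets the study team see unblinded aggregate data during recruitment. At stake are the credibility of the primary p-value, power in a 60-patient study, and whether readers get an effect size with its uncertainty.

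**Working it through.** **1. The wording, side by side**

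| Place | Tests allowed | Pairing |
|---|---|---|
| Protocol 7, SAP 1.3 | non-parametric only | paired or unpaired |
| SAP 3.2 | parametric or non-parametric | between groups, so unpaired |

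A paired test works within an arm and cannot compare randomised groups, so that word is loose. The real conflict is whether a t-test is allowed. A mean difference with CI also matches neither a rank test nor medians and ranges.

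**2. The plan's power figure**

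The documents give n = 30 per arm, power 80%, alpha 0.05 and an effect of 30%. They give no SD, scale or sidedness, so the figure cannot be reproduced, only solved backwards. For a ratio of 0.70, with |ln 0.70| = 0.3567:

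SD = 0.3567 / [√(2/30) × (z for alpha + z for power)]

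- two-sided: 0.3567 / (0.2582 × 2.8016) = 0.493
- one-sided: 0.3567 / (0.2582 × 2.4865) = 0.556

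The noncentral t gives 0.485 and 0.549. The 80% is thus neither confirmed nor refuted.

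**3. Why the scale matters**

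Let c be the log change. Then D3 − D1 = D1 × (e^c − 1). For the same proportional change, a patient with k times the baseline contributes k times the difference. Baseline spread therefore becomes noise in the raw difference. It cancels in the log change.

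**4. Power by simulation**

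Assumptions, not in the documents: log-normal D-dimer, ratio 0.70, no dropout, two-sided 0.05, baseline log-SD 0.25 to 1.2, correlation r of log change with log baseline from 0 to −0.5, no age effect. There were 30 per arm and 6,000 trials per setting. Ranges run over baseline SD and r.

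| Analysis | Log-change SD 0.40 | 0.485 | 0.60 |
|---|---|---|---|
| Mann-Whitney, raw difference | 70-89% | 57-76% | 43-57% |
| Welch t, raw difference | 29-89% | 23-74% | 18-55% |
| t-test, log change | 92-93% | 79-81% | 61-63% |
| Log model, baseline + age stratum | 92-98% | 79-90% | 61-74% |
| Log model minus raw Mann-Whitney (points) | 3-27 | 4-33 | 4-31 |
| Same gap at r = 0 (points) | 3-14 | 4-19 | 4-16 |

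At r = 0 the model does not beat a plain t-test on log change. Its further gain depends on change being correlated with baseline.

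**5. The open choice of test**

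Under the same effect, the two raw-difference tests fall on different sides of 0.05 in 5-17% of trials at baseline log-SD up to 0.5, and in 18-42% at 0.8 to 1.2. With no true effect, always taking the smaller p-value gives a type I error of about 6-7% instead of 5%.

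**6. Leaving out the age strata**

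Blocking balances age between arms, but an unadjusted test keeps age variation in its error term. If age explains a share R² of the variance in log change, a z-test on log change rejects under the null with probability 2Φ(−1.96/√(1 − R²)):

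- R² = 0.1: 2Φ(−2.066) = 3.9%
- R² = 0.2: 2Φ(−2.191) = 2.8%

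Simulated raw Mann-Whitney (10,000 null trials per setting) gave 4.5-5.1%, 3.6-4.2% and 2.6-3.1% at R² of 0, 0.1 and 0.2. The log model stayed at 4.5-5.4%.

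**7. The responder comparison**

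Take a median placebo change of zero and a median TRV027 ratio of 0.70. The response probability is then Φ(−0.3567/SD) on placebo, i.e. 0.186, 0.231 and 0.276 at SD 0.40, 0.485 and 0.60, against 0.50 on TRV027. Exact power at 30 per arm is 65%, 48% and 33% for Fisher's test, and 74%, 58% and 43% for chi-square.

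**The case against.** The strongest reply is that an unadjusted rank test of change is valid in a randomised trial. The null results above support this: it is close to 5%, or conservative if age predicts change. Both passages that define the primary comparison say non-parametric, so SAP 3.2 is the outlier, and aligning it would settle the wording. The disagreement rates in step 5 were computed with a true effect. Much of the larger range is Welch losing power on skewed data, where plots would usually steer the analyst to the rank test. The false-positive cost is modest even at worst.

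A smaller repair also exists. Mann-Whitney on the Day 3/Day 1 ratio has 77-79% power at log-change SD 0.485, close to the 79-81% of the log-change t-test, and needs no new model. Finally, a log model replaces a mean change with a ratio, and the responder analysis already gives one relative-scale comparison.

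Most of this stands as a limit on size. It does not remove the defect. The wording still permits two tests, no rule chooses between them, and no between-arm estimate is planned. The responder comparison is supplementary, names no test or between-arm effect, and discards information. Even the smaller repair requires leaving the raw difference.

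**Conclusion.** The concern holds, and the plan should be changed. The conflicting test descriptions, the missing rule, the unused baseline and strata, and the absent between-arm estimate rest on the text alone.

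The sizes are conditional on log-normal D-dimer, a proportional effect and the SDs shown. On those assumptions raw Mann-Whitney gives up 3 to 33 points of power against the log model, and 3 to 19 points if change is unrelated to baseline. They do not carry over to a constant absolute shift. Type I error from choosing between tests is at worst about 6-7%, so the main harm is an undefined primary result and lost efficiency rather than gross false positives. The sample size is not shown to be wrong.

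**What to change.** In SAP 1.3 and 3.2, with matching wording in Protocol 3.1 and 7:

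- Name one primary analysis: linear regression of log Day 3 D-dimer on treatment, log baseline D-dimer and age stratum, two-sided 0.05, reported as the TRV027/placebo ratio of geometric means with 95% CI.
- Drop the paired option and the open choice of test for the primary endpoint.
- Add a between-arm column to Table 10 (ratio, 95% CI, p-value).
- Keep Mann-Whitney on the Day 3/Day 1 ratio as a sensitivity analysis, and label the responder comparison supportive.
- Set a rule for values below the assay limit before taking logs.
- Date the change before anyone choosing the model sees the unblinded aggregates, or record who had seen them.
- Restate the power sentence (Protocol 7, SAP 1.5) as a ratio of 0.70 with sidedness, SD and source, and say which SD it is. For this model, 80% two-sided needs a residual log-SD of about 0.48. As residual SD = SD × √(1 − r²), the unadjusted log-change SD is about 0.48, 0.505 or 0.55 at r = 0, −0.3 or −0.5. Quoting the unadjusted SD is the conservative choice.

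The cost is wording, one table column and a short protocol amendment, with no new patients or data. The estimand becomes a ratio instead of a mean change. If change is uncorrelated with baseline, the model has about 1 point less power than a t-test on log change.

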1.5 Study sample size

The sample size (30 each group) provides 80% power (alpha 0.05) to detect a 30% reduction in the D-dimer level. Subjects will be block randomised based on age (<60, 60-69, >69 years).

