Total Bilirubin						
LDH						
Haptoglobin						
Creatinine						
BNP						
Troponin						
Ferritin						
Pro-calcitonin						
Glucose						

Table 11 Categorical Outcomes

	Control		TRV027		
	Day 1 (Yes/No %)	Day 3 (Yes/No %)	Day 1 (Yes/No %)	Day 3 (Yes/No %)	
Inotrope requirement					
DDimer response (>30% reduction)	NA		NA		

NA=not applicable

Table 12 vital signs and cardiovascular monitoring

	Screening [N=] % or Median (range)	Day 1 [N=] % or Median (range)	Day 3 [N=] % or Median (range)	Day 5 [N=] % or Median (range)
Pulse (Bpm)				
Diastolic blood pressure (mmHg)				
Systolic blood pressure (mmHg)				
Oxygen saturations (%)				
Temperature

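### SAP 3.2 relies on a 30% responder comparison to help separate statistical from clinical significance, but at 30 per arm that comparison has roughly 40-62% power at the planned effect, and no between-arm confidence interval is planned

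*SAP*

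**What the plan says.** The only power statement concerns D-dimer itself. SAP 1.5 reads: "The sample size (30 each group) provides 80% power (alpha 0.05) to detect a 30% reduction in the D-dimer level". Protocol section 7 gives the same numbers but speaks of a 30% change. Neither document gives an SD, a scale, the sidedness of alpha or an expected change on control.

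SAP 3.2 plans two analyses of the Day 3 data. The first takes each patient's difference from baseline, gives a mean with 95% CI within each arm, and compares the arms by a parametric or non-parametric test. The second is introduced as an addition: "a 30% reduction in DDimer will be considered a response". Proportions with 95% CIs are calculated and compared. Table 11 labels the row "DDimer response (>30% reduction)"; the gap between at least 30% and more than 30% is immaterial for a continuous marker. The section then closes: "The results of these two analyses will provide sufficient evidence to differentiate between statistical and clinical significance".

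No test, alpha, power or rule for discordant results is given for the responder comparison. Table 10 has a difference column inside each arm and no between-arm column.

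**The concern.** The closing sentence of SAP 3.2 gives the responder comparison an interpretive job: beside the continuous test, it is meant to show whether a statistical difference matters clinically. Three features make it unfit for that.

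- The cut is the planning effect. If control does not change and TRV027 lowers D-dimer by the planned 30%, the typical treated patient sits on the cut, and about half fall on each side.
- It is the same Day 3 change, dichotomised. It describes individual changes, but it carries less information about the treatment effect than the continuous comparison does.
- The quantity from which clinical relevance is normally read, the between-arm effect with its interval, is not planned.

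At stake is a real effect of the planned size being reported as statistically significant but of doubtful clinical relevance, only because the second comparison was too weak to confirm it.

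**Working it through.** **Inputs from the documents.** 30 per arm, alpha 0.05, 80% power, 30% reduction (SAP 1.5, Protocol section 7); responder cut 30% (SAP 3.2).

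**Assumptions, because the documents are silent.** Two-sided alpha; effect read as a between-arm ratio of 0.70; normally distributed log change; no change on control in the base case; all 30 per arm evaluable. The last is a best case, since SAP 2.2 restricts the analysis set to patients who received the full course and SAP 2.4 allows no imputation.

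**Step 1: the plan's own figure.** The 80% cannot be checked independently without an SD, so I solve for the SD that makes it true. A two-sided t-test with 30 per arm has 80% power at a standardised difference d = 0.736. With ln(0.70) = -0.357, SD = 0.357/0.736 = 0.485. On the percent-change scale, SD = 0.30/0.736 = 0.408. The cut is d SDs below no change on either scale, so the results below do not depend on the scale.

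**Step 2: response rates.** Control: Φ(-0.736) = 0.231. TRV027: Φ(0) = 0.50.

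**Step 3: responder power by exact enumeration at 30 per arm.**

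| Control Day 3/Day 1 | Responders, control v TRV027 | Fisher | Chi-square |
|---|---|---|---|
| 0.70 | 50% v 77% | 48% | 58% |
| 0.84 | 35% v 64% | 52% | 62% |
| 1.0 | 23% v 50% | 48% | 58% |
| 1.2 | 13% v 35% | 41% | 52% |
| 1.43 | 7% v 23% | 26% | 43% |

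Using the normal-approximation SD (0.493) lowers these slightly: 47% and 57% with no control change, and 40% for Fisher at 1.2. Over 0.70-1.2 the range is therefore about 40-62%. In the base case, 80% responder power would need about 50-51 per arm, or 57-58 with a continuity correction.

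**Step 4: discordance.** In 40,000 simulated trials at the target effect with no control change, the log-scale t-test was significant and the responder test was not in 33% (Fisher) or 24% (chi-square). With Mann-Whitney as the continuous test the figures are 30% and 21%. Against t-test power of 79.8%, 0.329/0.798 = 41% and 0.236/0.798 = 30% of the trials that succeed on the continuous test are not confirmed. Over control changes of 0.70-1.2, with the t-test, discordance is 30-40% (Fisher) and 20-30% (chi-square).

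**Step 5: sensitivity to the SD.** With log SD 0.6, continuous power is about 62% and responder power 33-43%. With log SD 0.4 they are 92.5% and 65-74%. The responder comparison is the weaker one each time.

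**Step 6: what a between-arm interval would show.** SE = 0.485 × √(2/30) = 0.125. Using t = 2.00, exp(-0.357 ± 0.251) gives an expected ratio of 0.70 with 95% CI 0.54 to 0.90.

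**The case against.** The strongest objection is that no single figure belongs to this plan. The 48% and the one-third discordance need Fisher's test, a back-solved SD and no control change; an uncorrected chi-square gives 58% and about a quarter. This stands, and is why ranges are given.

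A second objection concerns the discordance. SAP 3.2 and Table 10 work with the absolute difference, Day 3 minus Day 1, whereas Step 4 tests the log change. With absolute differences and an assumed baseline log SD of 0.5 to 1.2 (not in the documents), discordance with Fisher is 12-25% (t-test) or 22-26% (Mann-Whitney), and with chi-square 9-18% or 15-18%. Part of the fall arises because continuous power itself drops to 35-66% or 62-72%. So the quarter-to-a-third figure applies to a log-scale analysis. Responder power is unchanged.

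Three stronger readings are tempting, and the documents do not support them.

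- *The responder result will contradict a true effect.* SAP 3.2 sets no alpha or success rule for it, reports proportions with CIs, and relies on the two analyses jointly. A non-significant result from an underpowered comparison is inconclusive.
- *Two efficacy tests without a hierarchy inflate the false-positive rate.* Protocol 3.1 and SAP 1.3 name one primary endpoint, SAP 3.2 adds the responder analysis to it, and nothing says that either test alone would support a claim.
- *The responder analysis is worthless.* Proportions describe individual changes that a mean does not, so they merit reporting.

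**Conclusion.** The point holds as a limited one: the closing claim of SAP 3.2 is unsupported. If the trial has its stated 80% power for a 30% effect, the responder comparison has about 48% (Fisher) to 58% (chi-square) power with no control change, and about 40-62% over control changes of 0.70-1.2 times baseline. No case tried with the SD tied to the stated power exceeded about 62%. On a log-scale analysis, roughly a quarter to a third of trials at the target effect would be significant on the continuous test and unconfirmed on the responder test. These figures rest on a back-solved SD, two-sided alpha and 30 evaluable patients per arm; fewer evaluable patients would lower the power.

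The absence of a planned between-arm interval needs no assumption: it follows from SAP 3.2 and Table 10. The primary comparison is untouched; what fails is the planned route from it to a statement about clinical significance.

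**What to change.** 1. Delete the last sentence of SAP 3.2.
2. Add to SAP 3.2, and as a column in Table 10, a between-arm estimate with 95% CI for the Day 1 to Day 3 D-dimer change. It should match the test chosen: for example, the ratio of geometric mean Day 3/Day 1, or a Hodges-Lehmann estimate on the log scale if the comparison is non-parametric.
3. State that clinical relevance is judged from the whole interval, not from whether the point estimate passes 0.70. A point-estimate rule would repeat the problem: with a true ratio of 0.70 about half of estimates fall short of it, and about 30% of trials are significant with an estimate weaker than 0.70.
4. Report responder proportions descriptively, with a CI for their difference and no significance test.

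The cost is a few lines of SAP text, the added column in Table 10 and a difference with CI in Table 11. No new data, visits or patients are needed. The downside is the loss of a responder p-value.
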